 - a. In this study, we propose a single-blinded (Invisalign faculty) randomized prospective paralleled clinical trial to investigate effects of AcceleDent vibration therapy on the efficiency of tooth movement, on the activation of gingival crevicular fluid biomarkers and on patient discomfort in conjunction with accelerated Invisalign therapy. Enrolled subjects will be randomly allocated into one of 3 groups: Standard Invisalign therapy (G1-control), Accelerated Invisalign therapy + vibration (G2) and Accelerated Invisalign therapy without vibration (G3). Patients allocated to the standard Invisalign group will change aligners every 2

weeks while the both intervention groups will change aligners every 4 days. Patients allocated to the vibration group will receive an AcceleDent Aura device and bite down on the mouthpiece for 20 minutes/day. The AcceleDent Aura device vibrates at a .25N (25 grams) force level with a 30 Hz frequency. Data collection will include intra oral scans of both the maxillary and mandibular dentition at 5 different time points: TO (baseline), T1 (4 days), T2 (14 days), T3 (6 weeks) and T4 (12 weeks). In addition, PerioPaper strips will be used to sample gingival crevicular fluid at each of the time points listed above. Research subjects will also be asked to complete a daily diary regarding their pain level during treatment. Treatment plans for enrolled patients will be created using Invisalign's proprietary software: Clincheck Pro®. To reduce treatment plan variability and reduce potential sources of error, [name], who is an "Elite Top 1% Invisalign provider" and also a member of the exclusive North American Invisalign Clinical Advisory Board, will approve each treatment plan. [name] will also be blinded to any patients participation within the study in order to eliminate potential bias.

2. Recruitment:

- a. Participants will be conveniently recruited from the sample population of individuals seeking Invisalign orthodontic therapy within the UNC Graduate Orthodontic Clinic. Benefits for participants will include complementary vibration therapy using the AcceleDent Aura device, which is an estimated value of \$800. Financial reimbursement will also be offered to offset any parking fees associated with the study.
- 3. Power Analysis:

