 - f. Chronic daily use of any non-steroidal anti-inflammatory medication, estrogen, calcitonin, or corticosteroids.
 - **g.** History of use or current use of any bisphosphonate medication or other medication for treatment of osteoporosis.
 - h. Current smoker (must not have smoked in the last 6 months).
 - i. Failing to comply with research protocols
- 8. Arms:
 - a. Control Group (G1): 14 patients, standard Invisalign therapy with 2 week aligner schedule
 - a. Intervention Group (G2): 14 patients, accelerated Invisalign + vibration
 i. AcceleDent device 20 minutes/day per manufacturer's instructions

b. Intervention Group (G3): 14 patients, accelerated Invisalign + no vibration

- 7. Clinical Trial Protocol:
 - a. Visit #1: Clinical Screening with UNC Orthodontic Faculty (clinical purposes only)
 - i. Brief discussion of findings with patient and eligibility for Invisalign
 - b. Visit #2: Clinical exam and records (clinical purposes only), 30 days post visit #1
 - i. Completion of medical history
 - ii. Completion of extra and intra oral exams
 - iii. Completion of alginate impressions
 - iv. Photographs (extra and intra oral)
 - v. Xrays- Panoramic and Cephalometric
 - c. Visit #3: Treatment Plan Presentation (Experimental Baseline), 60 days post visit #1

- i. Clinical Procedures:
 - 1. Treatment plan presentation
 - a. Each treatment plan will be approved by [name] who will be blinded to a patient's study participation
 - 2. Invisalign impressions with PVS material
- ii. Research Procedures:
 - 1. Study recruitment
 - 2. Informed Consent
 - 3. iTero intraoral scan
 - 4. Completion of the Inclusion/Exclusion Case Report Form
- d. Visit #4: (120 days post visit #1/Day #1 of active treatment)
 - i. Clinical Procedures:
 - 1. Intraoral exam and intraoral photographs
 - 2. Deliver aligner number 1 and usage instructions
 - ii. Research Procedures:
 - 1. Deliver AcceleDent Aura device along with instructions
 - 2. Collection of gingival crevicular fluid biomarkers
 - 3. Completion of Faces Pain Scale
 - 4. Deliver daily diaries
- e. Visit #5: (125 days post visit #1/ Day #5 of active treatment)
 - i. Clinical procedures:
 - 1. Deliver aligners 2-4 to accelerate Invisalign groups and aligner schedule instructions
 - ii. Research Procedures:
 - 1. iTero intraoral scan
 - 2. Collection of gingival crevicular fluid biomarkers
 - 3. Completion of Faces Pain Scale and Adverse Event Form
- f. Visit #6: (134 days post visit #1/Day #14 of active treatment)

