 - i. Clinical procedures
 - 1. Intraoral exam and intraoral photographs
 - 2. Place attachments (35% phosphoric acid etch, L-pop selfetching primer, composite resin, LED light curing for 30 secs)
 - **3.** Deliver more aligners: 2-3 to control group and 5-11 to intervention groups (accelerated Invisalign)
 - ii. Research Procedures:
 - 1. iTero intraoral scan
 - 2. Collection of gingival crevicular fluid biomarkers
 - 3. Completion of Faces Pain Scale and Adverse Event Form
- g. Visit #7: (176 days post visit #1/6 weeks of after treatment)
 - i. Clinical procedures:
 - 1. Intraoral exam and intraoral photographs

- ii. Deliver more aligners: 4-6 to control group and 11-21 to intervention groups (Accelerated Invisalign)
- h. Research:
 - 1. iTero intraoral scan
 - 2. Collection of gingival crevicular fluid biomarkers
 - 3. Completion of Faces Pain Scale and Adverse Event Form
- i. Visit #8: (218 days post visit #1/12 weeks of active treatment) (End of clinical study)
 - i. Clinical Procedures:
 - 1. Intraoral exam and photographs
 - 2. Deliver more aligners to both control (7-12) and intervention groups (21-30)
 - **3.** Deliver AcceleDent Aura devices to participants in control and non-vibration intervention group.
 - ii. Research Procedures:
 - 1. iTero intraoral scan
 - 2. Collection of gingival crevicular fluid biomarkers
 - 3. Completion of Faces Pain Scale and Adverse Event Form
- j. Visit #9: (260 days post visit #1)
 - i. Clinical Procedures:
 - 1. Intraoral exam and photographs
 - 2. Deliver any remaining aligners
 - 3. iTero Scan for any necessary revisions
- k. Visit #10: (302 days post visit #1)
 - i. Clinical Procedures:
 - 1. Intraoral exam and photographs
 - 2. Deliver revision aligners as needed
- l. Visit #11: Treatment complete, ensure patient satisfaction
 - i. Clinical Procedures:
 - 1. Intraoral exam and photographs
 - 2. Completion of alginate impression
 - 3. Completion of post tx pano and cephalometric xrays
 - 4. Deliver Essix retainers to prevent relapse
- 8. Data Collection:
 - b. 3D intraoral scanning protocol
 - i. T0- baseline
 - ii. T1- 4 days
 - iii. T2-14 days
 - iv. T3-6 weeks
 - v. Tfinal- 12 weeks
 - c. Gingival Crevicular Fluid Sampling
 - i. T0- baseline
 - ii. T1-4 days

- iii. T2-14 days
- iv. T3-6 weeks
- v. Tfinal- 12 weeks
- d. Orthodontic Pain Assessment
 - i. Daily dairy using Faces Pain Scale
- 9. Monitoring Compliance:
 - a. Daily diary usage log
 - b. AcceleDent Fast Trac usage report
- 9. Adverse Events:

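### The day counts for Visits #7 and #8 put T3 and T4 at 8 and 14 weeks after the first aligner, not the stated 6 and 12 weeks

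*Combined protocol and SAP*

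**What the plan says.** Methods, Study Design, places the scans after baseline at "T1 (4 days), T2 (14 days), T3 (6 weeks) and T4 (12 weeks", with gingival crevicular fluid (GCF) sampled on the same occasions. The abstract and the Data Collection item repeat these times, and the objective covers the first 12 weeks.

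The Clinical Trial Protocol item dates each visit twice, by days since Visit #1 (screening) and by time on treatment:

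- "Visit #4: (120 days post visit #1/Day #1 of active treatment": aligner 1 is delivered.
- "Visit #5: (125 days post visit #1/ Day #5 of active treatment": "Deliver aligners 2-4 to accelerate Invisalign groups and aligner schedule instructions".
- "Visit #6: (134 days post visit #1/Day #14 of active treatment": "Deliver more aligners: 2-3 to control group and 5-11 to intervention groups (accelerated Invisalign".
- "Visit #7: (176 days post visit #1/6 weeks of after treatment": aligners 4-6 go to control and 11-21 to the accelerated arms.
- "Visit #8: (218 days post visit #1/12 weeks of active treatment": the end of the clinical study.

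Control aligners are worn for 14 days each and accelerated aligners for 4. The Statistical Analysis item has time as a main effect. It plans comparisons of the five occasions inside each arm, and of the arms at each occasion.

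**The concern.** For Visits #7 and #8 the two dates on the same line disagree by two weeks, and the visit list does not say which one governs. These are operative dates: staff could book from either.

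Booking by day count would put T3 and T4 two weeks late. It would also leave patients without a new aligner before Visit #7, so the T3 scan, GCF sample and pain score would describe a period after scheduled wear instead of the middle of treatment. That changes what T3 means in the within-arm time comparison. It would also put the wrong number of days under any movement rate computed from the nominal weeks.

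**Working it through.** **Elapsed time.** Formula: visit day minus 120, the day aligner 1 is delivered.

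| Visit | Day since Visit #1 | Days since aligner 1 | Planned time point | Difference |
|---|---|---|---|---|
| #5 | 125 | 125 - 120 = 5 | T1 = 4 | +1 |
| #6 | 134 | 134 - 120 = 14 | T2 = 14 | 0 |
| #7 | 176 | 176 - 120 = 56 (8 weeks) | T3 = 42 | +14 |
| #8 | 218 | 218 - 120 = 98 (14 weeks) | T4 = 84 | +14 |

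**Can another clock rescue the labels?** Counting day 120 as Day #1 gives Day #57 and Day #99, which does not help. Counting from Visit #6 does reproduce them: 134 + 42 = 176 and 134 + 84 = 218. But Visit #6 is itself labelled two weeks into active treatment, and Visit #8 is labelled as 12 weeks of active treatment. One clock cannot give both.

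**Which figure slipped?** The aligner supply is an independent check.

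- Control: aligners 1-3 last 3 x 14 = 42 days; 1-6 last 6 x 14 = 84 days.
- Accelerated: aligners 1-11 last 11 x 4 = 44 days; 1-21 last 21 x 4 = 84 days.

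These fit visits at 42 and 84 days, not 56 and 98.

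**What happens if the day counts are followed?** Aligner 11 is listed at both Visit #6 and Visit #7; I take it as dispensed at Visit #6. In the accelerated arms aligner 2 starts at Visit #5, 5 days in.

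- Control supply ends at day 42. Gap before Visit #7: 56 - 42 = 14 days.
- Accelerated supply ends at 5 + 10 x 4 = 45. Gap: 56 - 45 = 11 days. If aligner 11 came only at Visit #7, supply would end at 5 + 9 x 4 = 41 and the gap would be 15 days.
- Before Visit #8: control 98 - (56 + 3 x 14) = 0 days; accelerated 98 - (56 + 10 x 4) = 2 days.
- Time from last aligner change to T3: control 56 - 28 = 28 days; accelerated 56 - 41 = 15 days. With visits at days 4 and 42 these would be 42 - 28 = 14 and 42 - 40 = 2 days.

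**Rates.** Suppose movement follows the aligners worn and is divided by nominal time. The ratio to the planned pace is then 42/42 (0%) for control at T3, 44/42 (+4.8%) for accelerated at T3, and 84/84 (0%) for both at T4. Suppose instead that movement continued at full pace through the gaps. The ratios would be 56/42 (+33%) and 98/84 (+17%). The documents support neither assumption, and the plan defines no denominator.

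**The case against.** The best defence is that the intended schedule is clear. The abstract, Study Design, Data Collection, the week labels and the aligner supply all agree. The odd one out is a secondary count from a screening visit held for clinical purposes. On this view the point is clerical, and harm requires staff to follow that count against everything else. Most of this stands as evidence of which figure is wrong. It does not make the error harmless, because the wrong figures stand in the list from which visits would be booked.

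Four stronger readings are tempting, and the documents do not support them:

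- **The vibration contrast is biased.** All arms share the visit calendar, and G2 and G3 share the aligner schedule, so comparisons at the same visit stay equally timed.
- **Rates are overstated by 33% and 17%.** That needs full-pace movement with no new aligner, which the plan nowhere states.
- **T1 is planned at 5 days instead of 4.** With Visit #4 as Day #1, the Day #5 label means 4 elapsed days and matches T1. Only the count of 125 is off, by one day.
- **The two baseline dates are a second arithmetic error.** The baseline scan is at Visit #3 (day 60), while the first GCF sample and pain score are at Visit #4 (day 120), 120 - 60 = 60 days later. Study Design implies a common T0, so there is a wording mismatch. But Visit #3 is explicitly labelled the experimental baseline, and no planned analysis pairs scan with GCF. Any drift over those 60 days is unsized, probably small, and should be balanced by randomisation.

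**Conclusion.** The day counts for Visits #7 and #8 are wrong as written. Each is 14 days past its stated time point, and no single clock reconciles them. The likely cause is adding 42 and 84 days to Visit #6 instead of Visit #4. Visit #5 carries a separate one-day slip.

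The arithmetic is certain; the consequence is conditional. If visits are booked by day count, T3 measures fall after scheduled wear has ended, with about 14 days (control) or 11 days (accelerated) lacking a new aligner. This assumes that aligners are changed on schedule and that aligner 11 is dispensed at Visit #6. What is exposed is the meaning of T3 and T4 in the within-arm comparisons and any rate per nominal week; the size of the rate error is unknown. The documents do not show how visits were actually booked. The correction should be made because it is cheap and the dates are operative.

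**What to change.** 1. Set Visit #7 to 120 + 42 = day 162 and Visit #8 to 120 + 84 = day 204. If the 42-day spacing of the later clinical visits is kept, Visits #9 and #10 become days 204 + 42 = 246 and 246 + 42 = 288.
2. Set Visit #5 to 120 + 4 = day 124, which matches its own label and T1.
3. Label Visits #5 to #8 as 4, 14, 42 and 84 elapsed days since aligner 1, and state that these govern. This also removes the off-by-one at Visit #6, where day 134 would be Day #15 if day 120 is Day #1.
4. Add one sentence to the Statistical Analysis item: any movement rate, including a rate between two successive scans, uses the actual days elapsed between those scans. This holds whichever schedule staff followed, so it remains useful if visits have already taken place.

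The cost is up to five day counts, the visit labels and one sentence.

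Optional, and not needed to correct the arithmetic: take the baseline research scan at Visit #4, before aligner 1 is placed, so that scan, GCF and pain share one T0. No scan is added, but Visit #4 becomes slightly longer.

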 - a. Our study will have 3 groups for evaluation: G1 control (Invisalign on a 2week aligner schedule) and 2 intervention groups, G2 and G3 (each on an accelerated 4 days aligner schedule). The only difference between the intervention groups will be the use of vibration (G2 with vibration vs G3 without vibration). The expected rate of tooth movement for G1 will be .04mm/day (.25mm/week or .5mm/2 weeks) while the expected rate of tooth movement for G2 and G3 will be .28mm/day (.5mm in 4 days). The standard deviation is assumed 0.1 for three groups. Based on our sample calculation to achieve an adequate power, we will attempt to recruit a total of 42 patients to account for a dropout rate of 30%. Ideally, we would like to have a total sample size of 21 patients to ensure each of 3 study groups will have 7 patients, which will achieve more than 0.8 power even under a Bonferroni correction for multiple comparisons.
- 4. Randomization:
 - a. Our patients will be randomly allocated into the 3 groups based on a block randomization with size 6. The list will be independently generated by our study biostatistician.
- 5. Type I error and statistical significance:
 - a. P values less than .05 will be considered statistically significant in the overall test
- 6. Inclusion Criteria:
 - a. Males or females over the age of 18 years old desiring orthodontic treatment.

- b. Adult dentition with all upper and lower front teeth present and any premolar and molar combination in the upper posterior of two teeth on each side.
- c. Normal pulp vitality and healthy periodontal tissues as determined by intraoral exam.
- d. Good health as determined by medical history.
- e. Willingness and ability to comply with study procedures, attend study visits, and complete the study.
- f. The ability to understand and sign a written informed consent form, which must be signed prior to initiation of study procedures.
- 7. Exclusion Criteria:
 - a. Patient under the age of 18 years old
 - b. Patients diagnosed with systemic diseases such as diabetes, hypertension (high blood pressure), temporomandibular disorders (jaw disorders), or craniofacial syndromes.
 - c. Severe malocclusions that would require adjunctive procedures other than Invisalign. These include impacted teeth, closure of extractions spaces.
 - d. Significant periodontal disease (> 4mm pocket depth or >2 mm of recession on upper anterior teeth).
 - e. Active caries not under care of either a dentist or periodontist.

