 - a. Patients who experience an adverse event or reaction such as: uncontrolled pain or allergy will be disenrolled from the study and allowed to continue Invisalign therapy using the standard two-week aligner schedule. In addition, non-compliant patients will be disenrolled from the study and recommend to continue Invisalign therapy using the standard protocol.
- 10. Data Analysis:
 - a. Tooth leveling and alignment
 - i. Little's Index
 - b. Tooth rotations and translations
 - i. Euler's Law of Motion (6 degrees of freedom)
 - ii. 3D surface mapping
 - c. Alternative measurement options
 - i. Screw Method
 - d. Inflammation biomarkers within gingival crevicular fluid
 - i. ELISA
 - e. Orthodontic Pain Assessment
 - i. Faces Pain Scale
- 11. Statistical Analysis:
 - a. In order to complete statistical analysis for maxillary and mandibular dentition, we will compare the five time points within each group as well as the three groups across each time point.
 - b. Our primary statistical method will be a three-way repeated measurement ANOVA, with the main effects being: vibration, aligner schedule, and time. The ANOVA measurement will identify significant differences within the data and the post hoc comparison will determine which specific variables are involved. In order for a relationship to be considered statistically significant, the p-value must be less than .05.
 - c. One additional method for statistical analysis could be a survival analysis which would be more favorable in the case our study experiences a high volume of drop-outs during treatment.
- 12. Patient Confidentiality:
 - a. Records related to this research study that involve perennial information will only be accessible by the primary research committee and direct assistants. Records will be stored on encrypted, password-protected computer hard drives. A 3-digit code number will be used rather than the subject's name to identify the specific data related to his/her involvement in the study. Only the research investigators will have access to the file that links personal

information to the 3-digit codes, and this file will be stored in a separate location from the actual research data.

Project Timeline:

Item	Date
Study Design; IRB submission ([name])	Spring 2016
Background Research	March 2016
Loose conceptual framework	March 2016
Presentation	April 2, 2016
Protocol	May 16, 2016
IRB approval	May 2016
Select study population	August 2016
Clinical Trial	November 2016

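### Little's Index cannot fall below zero, so a null G2 versus G3 result on it at T3 or T4 may reflect the instrument and not vibration

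*Combined protocol and SAP*

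**What the plan says.** Section 10 (Data Analysis), item a, names one measure of leveling and alignment: "Little's Index". Item b adds rotations and translations in 6 degrees of freedom and 3D surface mapping, all from the same intraoral scans.

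Section 11 (Statistical Analysis), item a, says "we will compare the five time points within each group as well as the three groups across each time point". Item b makes a repeated-measures ANOVA on vibration, aligner schedule and time the main method. Section 11 does not tie either item to a particular outcome, so as written both apply to the index. Nothing is said about patients whose index is already zero.

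Section 3 (Power Analysis) gives the expected rates: "The expected rate of tooth movement for G1 will be .04mm/day (.25mm/week or .5mm/2 weeks" and "expected rate of tooth movement for G2 and G3 will be .28mm/day (.5mm in 4 days". It adds: "The standard deviation is assumed 0.1 for three groups".

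No minimum, maximum or expected baseline index is stated. The nearest criterion is item c of the Exclusion Criteria: "Severe malocclusions that would require adjunctive procedures other than Invisalign".

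**The concern.** An index that measures misalignment can improve only by its baseline value. After that it stays at zero while the clock runs on. If the patients in both accelerated arms reach zero before a scan, their index values agree at that scan whatever vibration did.

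G2 versus G3 is the only contrast that isolates vibration, and the Background makes that the central question: is vibration or the faster aligner schedule responsible for the reported acceleration? A null index contrast at 12 weeks could be reported as no effect of vibration when it shows only that both arms had finished aligning. The G1 contrast would be understated too, because G1 stays in range longer.

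**Working it through.** **Inputs from the documents.** Scans at days 0, 4, 14, 42 and 84. G1 rate .04 mm/day. G2 and G3 rate printed as .28 mm/day and also as .5 mm in 4 days. SD 0.1 (unit not stated; taken as mm/day). Planned evaluable patients: 7 per group.

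**Checking the plan's rates.** G1: .5/14 = .036 mm/day, which rounds to .04. G2 and G3: .5/4 = .125 mm/day, not .28. The two G2/G3 figures contradict each other and must be reconciled. I use .125 below because the slower rate is the more cautious choice for this point.

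**Cumulative movement = rate x days.**

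| Rate (mm/day) | T2, day 14 | T3, day 42 | T4, day 84 |
|---|---|---|---|
| .04 (G1) | .56 mm | 1.68 mm | 3.36 mm |
| .125 (G2, G3) | 1.75 mm | 5.25 mm | 10.5 mm |
| .28 (G2, G3 as printed) | 3.92 mm | 11.76 mm | 23.52 mm |

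If the index falls at the stated rate, a 5 mm baseline reaches zero on day 5/.125 = 40, on day 5/.28 = 18, or on day 5/.04 = 125.

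**Assumptions that the documents do not supply.**
- The index is a sum of displacements in mm, with zero meaning perfect alignment.
- Mean baseline is 3, 5, 7 or 10 mm, gamma distributed, with SD 40% of the mean.
- G3 moves at .125 mm/day and G2 25% faster. The plan gives both arms the same expected rate, so a difference has to be assumed.
- Between-patient SD is .03 mm/day, with the plan's 0.1 as an alternative. Negative rates are set to zero.
- The index falls at a fraction f of the stated rate; f = 1 means mm for mm.

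**Formula.** Recorded change by day d = min(baseline, f x rate x d). Share shown = (mean recorded change in G2 minus that in G3) / (the same difference without the floor). The result depends on f x d, so half rate at day 84 equals full rate at day 42. Simulated values carry an uncertainty of about one percentage point.

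**Share of the true G2-G3 difference that the index shows.**

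| Case | 3 mm | 5 mm | 7 mm | 10 mm |
|---|---|---|---|---|
| Full rate, T2 | 79% | 96% | 99% | 100% |
| Full rate, T3 | 6% | 33% | 61% | 84% |
| Full rate, T4 | 0% | 2% | 11% | 33% |
| Full rate, T4, SD 0.1 | 8% | 15% | 23% | 37% |
| Half rate, T4 | 6% | 33% | 61% | 84% |
| Quarter rate, T4 | 48% | 84% | 95% | 99% |

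**G3 patients at zero by T4** (G2 is higher in each case).

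| Case | 3 mm | 5 mm | 7 mm | 10 mm |
|---|---|---|---|---|
| Full rate | 100% | 95% | 83% | 57% |
| Full rate, SD 0.1 | 81% | 74% | 66% | 52% |
| Half rate | 90% | 57% | 30% | 11% |
| Quarter rate | 42% | 11% | 3% | 1% |

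**G1 versus G3 at T4**, full rate, SD .03: 12%, 29%, 49% and 71% of the true difference is shown.

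**Power, as a cross-check.** This uses 7 per arm, SD 0.1, two-sided alpha .05/3 = .0167, baseline SD 2 mm, and G2 at .25 against G3 at .125 mm/day. With a 6 mm baseline, power on the index is .38 at day 4, .34 at day 14, .12 at day 42 and .05 at day 84. With a 10 mm baseline it is .37, .38, .30 and .09. Power is low at the start, and by day 84 the floor removes most of what there was.

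**The case against.** Four points on the other side have weight.

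- **Other measures.** A reader might infer that the later scans cannot show any difference in rate. The documents do not support that. The same scans feed the 6-degree-of-freedom and surface-mapping measures, which have no such floor, and section 10 lists the index for alignment, not for rate. The point is confined to the index.
- **Baseline crowding.** A reader might also infer that most eligible patients will reach zero. No baseline index is given. Exclusion item c turns on the need for adjunctive procedures (impacted teeth, closing extraction spaces) and sets no crowding limit. The share at zero is therefore conditional on the assumed baseline.
- **Movement is not index reduction.** The plan states an expected rate of tooth movement and never says that the index falls mm for mm. The aligner schedule suggests slower alignment: at week 12 the accelerated arms have used 84/4 = 21 aligners, and numbers 21 to 30 are handed out. If alignment were spread evenly over 30 aligners, 30% of the baseline would remain at week 12. A 5 mm baseline would then fall at .7 x 5/84 = .042 mm/day, a third of .125. At a third of the rate, 66%, 86% and 96% of the difference is shown at T4 for 5, 7 and 10 mm, and 25% for 3 mm. The even spread is itself an assumption, because later aligners may move teeth that the index does not cover. The uncertainty is real in both directions.
- **Restricting the index to T0-T2.** This is a tempting remedy, since little is lost by day 14, but it is a poor trade. The window covers one G1 aligner and ends at the visit where attachments are placed. The baseline scan is listed at Visit 3 (day 60) and none at Visit 4 (day 120), so T0 to T2 spans 134 - 60 = 74 calendar days. With 7 per arm and a 25% effect, unadjusted power at T2 is about 43% at SD .03 (25% under Bonferroni) and about 8% at the plan's SD.

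**Conclusion.** The concern stands as a conditional one. If the index falls at about .125 mm/day and mean baselines lie between 3 and 10 mm, more than half of G2 and G3 are at zero by T4. The index then shows about 0% to 33% of a true G2-G3 difference (about 8% to 37% at the plan's SD). At half the rate the range is 6% to 84%, and at a quarter 48% to 99%, so with slow alignment and crowded patients the loss is small. If .28 mm/day were the intended rate, the floor would come sooner.

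The documents do not settle which case applies, and the plan has no rule that would let a reader of the results tell. A null G2-G3 index contrast at T3 or T4 therefore cannot by itself be read as absence of a vibration effect. The change is worth making, with medium confidence in how large the problem will prove.

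**What to change.** In sections 10 and 11:

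- Base rate comparisons at T3 and T4 on the 6-degree-of-freedom displacement that the plan already derives.
- Keep Little's Index at all five time points, adjusted for baseline index. State that its T3 and T4 values describe alignment attained and not rate.
- Report the baseline index, and the number of patients at zero at each scan, by arm.
- Add a sensitivity analysis of the index series that treats zeros as censored. It should stay a sensitivity analysis: with about 7 patients per arm, it says little if nearly all are at zero.
- Do not restrict the index analysis to T0-T2.
- In section 3, reconcile the two figures given for the G2/G3 rate.

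The cost is analysis-plan wording and a little extra analysis, with no new data. The small downside is that late index contrasts no longer count as evidence on rate.
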